pK _a	Acid dissociation constant at a Log scale (negative Log base 10 of the acid dissociation constant K _a)		
PKAS	PK analysis set		
PR interval	(ECG) The time from the onset of the P wave to the start of the QRS complex		
PT	Preferred term		
QRS interval	(ECG) The time required for stimulus to spread through the heart's ventricles		
QT interval	(ECG) The time from the beginning of the QRS complex to the end of the T wave		
QTcF	(ECG) Corrected QT interval by Fredericia		
RSI	Reference safety information		
SAD	Single-ascending dose		
SAE	Serious adverse event		
SAP	Statistical analysis plan		
SAR	Serious adverse reaction		
SD	Standard deviation		
SOC	System organ class		
SOP	Standard operating procedures		
SUSAR	Suspected unexpected serious adverse reaction		

Statistical Analysis Plan

CX842A2106

Version 1.0 final, 2023 Jan 16

T _{1/2}	Terminal elimination half-life
T _{lag}	Delay between the time of dosing and the time of appearance of plasma concentration
T _{max}	Time of occurrence of C _{max}
V ₂ /F	Volume of distribution following extravascular administration
WHO	World Health Organization
WHODrug	WHO drug dictionary

Statistical Analysis Plan

CX842A2106

Version 1.0 final, 2023 Jan 16

1. Introduction

This Statistical Analysis Plan (SAP) provides a detailed and technical description of the planned pharmacokinetic (PK) analyses and statistical evaluations of Cinclus Pharma AB's study CX842A2106: "A randomized, single dose, crossover study in healthy volunteers to investigate the relative bioavailability of linaprazan for a new oral tablet formulation of linaprazan glurate, and to assess the effect of food on the pharmacokinetics of linaprazan".

The SAP is prepared in compliance with the guidelines for Statistical Principles for Clinical Trials (ICH E9).

A full description of the investigational plan, eligibility criteria, assessments, etc. is given in the Clinical Study Protocol (CSP) CX842A2106 v2.0 dated 12 Oct 2022.

In case this SAP deviates from the statistical analysis described in the CSP, the reason for the deviation and/or alternative or additional statistical analyses will be documented in amendments to the CSP or in this SAP.

2. Study Objectives and Endpoints

This is a single-center, open-label, randomized, single dose, 3-way crossover study in healthy volunteers designed to evaluate the relative bioavailability of a new oral tablet formulation of linaprazan glurate in comparison to a previously studied oral tablet formulation under fasting conditions, and to assess the effect of a high-fat, high-calorie meal on the pharmacokinetics (PK) of linaprazan glurate and the active metabolite linaprazan after the administration of the new oral tablet formulation.

2.1 Primary Objectives

- To evaluate the relative bioavailability of linaprazan between the test formulation of linaprazan glurate
 and the previously studied reference formulation after the administration of single 100 mg doses in
 fasting conditions.
- To assess the effect of a high-fat, high-calorie meal, in comparison to fasting conditions, on the PK of linaprazan after the administration of single 100 mg doses of the test formulation.

2.2 Secondary Objectives

- To evaluate the relative bioavailability of linaprazan glurate between the test formulation of linaprazan glurate and the previously study reference formulation after the administration of single 100 mg doses in fasting conditions.
- To assess the effect of a high-fat, high-calorie meal, in comparison to fasting conditions, on the PK of linaprazan glurate after the administration of single 100 mg doses of the test formulation.
- To collect additional PK data on linaprazan glurate and linaprazan after single 100 mg doses of the test formulation.
- To assess the safety and tolerability of single oral doses of 100 mg of linaprazan glurate.

2.3 Primary endpoint

- Relative bioavailability of linaprazan for the test formulation vs. reference formulation of linaprazan glurate, based on the means ratios for the following PK parameters:
 - o Area under the plasma concentration vs. time curve (AUC) from time 0 to infinity (AUC_{inf})
 - o AUC from time 0 to the last measurable concentration (AUC_{last})

Statistical Analysis Plan

CX842A2106

Version 1.0 final, 2023 Jan 16

- Maximum plasma concentration (C_{max})
- Relative bioavailability of linaprazan under fed conditions vs. fasting conditions, based on the means ratios for AUC_{inf}, AUC_{last} and C_{max}.

2.4 Secondary endpoints (PK)

- Relative bioavailability of linaprazan glurate for the test formulation vs. reference formulation of linaprazan glurate, based on the means ratios for AUCinf, AUClast and Cmax.
- Relative bioavailability of linaprazan glurate under fed conditions vs. fasting conditions, based on the means ratios for AUCinf, AUClast and Cmax.
- Additional linaprazan glurate and linaprazan PK parameters after single 100 mg doses of the linaprazan glurate test formulation in fasting and fed conditions:
 - Time to Cmax (Tmax)
 - Delay between the time of dosing and the time of appearance of plasma concentration (Tlag)
 - o Terminal elimination half-life (T1/2)
 - o AUC percent extrapolation (AUCextrapol%)
 - Apparent clearance (CL/F)
 - Apparent volume of distribution (Vz/F)

2.5 Secondary endpoints (Safety)

- Frequency, seriousness, and intensity of adverse events (AEs).
- Clinically significant changes in electrocardiograms (ECGs), vital signs, safety laboratory measurements (clinical chemistry/hematology/coagulation) and physical examination findings.

3. Study Details

3.1 Study Design

The study will follow a 3-treatment, 3-period cross-over design where eligible study participants will be randomly allocated to one of six different treatment sequences. The participants will receive single doses of the Test and Reference formulations as given below:

•	Treatment A:	
•	Treatment B:	
•	Treatment C:	

The six treatment sequences are given in Table 1.

Table 1. Treatment sequences

Sequence no.	Sequence
1	ABC
2	ACB
3	BAC
4	BCA
5	CAB
6	CBA

Statistical Analysis Plan

CX842A2106

Version 1.0 final, 2023 Jan 16

3.2 Study population

The subjects participating in this study will be healthy male and female subjects 18–65 (both inclusive) years of age. More details regarding the study population, including inclusion and exclusion criteria, can be found in the CSP section 9.

3.3 Randomisation and Blinding

Block randomization (block size=6) will be used to generate the randomization list, which will show the assignment of subjects to 1 of the 6 treatment sequences shown on Table 1.

Randomisation lists for both parts of the study will be prepared by the DM provider and transferred to the Trial Master File (TMF) for archiving.

As this is an open label study, the treatment sequence to which each subject is allocated will be recorded in the eCRF. A computer-generated randomization list will be created using SAS Proc Plan, SAS Version 9.4 or later (SAS Institute, Inc., Cary, NC) or equivalent program. The randomization list will contain subject number, treatment sequence, period, and treatment.

The randomization list will be generated and kept by CRS.

No blinding procedures will be followed.

3.4 Number of Subjects

3.4.1 Sample Size

Approximately, 84 healthy volunteers are planned to be screened to achieve 54 randomized subjects (assuming a screening failure rate of approximately 37%), and at least 42 evaluable subjects. The number of subjects included in the trial is considered sufficient to describe and compare the PK of the Test formulation in relation to the Reference formulation.

3.5 Subject Replacement

Subjects who consent to study participation but discontinue study prior to IMP administration (dosing) may be replaced. If subjects are withdrawn after dosing, additional subjects may be included to obtain at least 42 evaluable subjects at the Sponsor's discretion after consultation with the Investigator.

4. Assessments

The overall schedule of assessments is given in Table 2. Details about each visit and the assessments made during the visit are given in the sections in the CSP that are listed in Table 2.

Table 2. Overall schedule of assessments

Visit → Assessment↓	CSP Section	Visit 1 Screening	Visit 2-4 Treatment visits			Visit 5 Telephone follow-up ¹
Day→	Day -1 to 2		Return to	7 days (±2 days) post- last dose		
Informed consent	11.2.1	Х				

Statistical Analysis Plan

CX842A2106

Version 1.0 final, 2023 Jan 16

Visit → Assessment↓	CSP Section	Visit 1 Screening	Visit 2-4 Treatment visits		Visit 5 Telephone follow-up ¹	
Eligibility criteria	9.4, 9.5	X	X ²			
Demographics	11.2.3	X				
Weight/height (BMI)	11.2.4	X				
Medical/surgical history	11.2.5	Х				
HIV, Hep B and C test	11.2.7	X				
FSH test ³	11 2 0	X				
Pregnancy test	11.2.8	X	X ⁴			
Urine drug screen	11.2.9	Х	X ⁴			
Alcohol test	11.2.10	Х	X ⁴			
Safety laboratory profile	11.4.3	Х	X		X	
Vital signs ⁵	11.4.4	X	X		X	
Physical examination	11.4.5	X	X		X	
12-lead safety ECG ⁶	11.4.2	X	X		X	
Randomization	9.9		X ⁷			
High-fat, high-calorie breakfast (fed condition)	10.5.2		Х			
IMP administration	10.5		X			
PK blood sampling ⁸	11.3.1		X	X	X	
Standardized meals	9.6.1		X			
Overnight stay in clinic			X			
Baseline symptoms ⁹	11.2.11	X				
Adverse events (AEs) ¹⁰	11.4.1				X	
Prior and concomitant medications	11.2.6	X				

BMI: Body mass index. CSP: Clinical study protocol. ECG: electrocardiogram. FSH: Follicle stimulating hormone. HIV: Human immunodeficiency virus.

- 1. Or after early withdrawal.
- 2. Confirmation of eligibility. Visit 2 only. Can be done on Day -1 or Day 1 prior to randomization.
- 3. Confirmation of menopause. Only in questionable cases at the discretion of the Investigator.
- 4. At Visit 2 only. Additional random alcohol and drug tests can be performed at subsequent visits at the discretion of the Investigator.
- 5. Resting systolic and diastolic blood pressure, pulse and body temperature. Blood pressure and pulse should be measured with the subject in a supine position, after 10 minutes of rest.
- 6. ECG time window between 4h and 4h30min after dosing.

Statistical Analysis Plan

CX842A2106

Version 1.0 final, 2023 Jan 16

- 7. At Visit 2 only.
- Collected within -01:00 hh:mm prior to IMP administration (pre-dose) and at 00:15, 00:30, 01:00, 01:15, 01:30, 02:00, 03:00, 04:00, 06:00, 08:00, 12:00, 14:00, 20:00, 24:00, 36:00, 48:00 and 72:00 hh:mm post-dose. Actual time for PK blood sampling must not deviate more than ±10% from the planned times.
- 9. Baseline symptoms will be recorded from the signing of the informed consent form (ICF) up until first dose on Day 1.
- 10. AEs will be recorded from dosing on Day 1 up until the follow-up visit (Visit 5), or early withdrawal.

4.1 Disposition and Other Supporting Assessments

4.2 Protocol Deviations

Deviations from the CSP should not occur. If deviations from the CSP occur, the implications and classification (minor or major) of each deviation will be decided and documented at the clean file meeting prior to database lock. If a subject is classified with a major protocol deviation, it will lead to exclusion of data from the PK analysis set and any such case should be clearly justified.

Major protocol deviations include:

- Significant non-compliance with study procedures
- Any serious unforeseen deviation in dosing of the subjects
- Vomiting or diarrhoea within 6 hours after dosing which could render the plasma concentration-time profile unreliable
- Intake of prohibited medication that may influence the PK results (i.e., known to interact with the PK of linaprazan glurate)

Subjects with minor protocol deviations may be included in the PK analysis set. If so, handling of minor protocol deviations in the PK analyses will be documented.

Blood sampling outside of the allowed timeframe will not be considered as a protocol deviation.

4.3 Demographic and Baseline Characteristics

The demographic and baseline data collected in this trial are gender, age, ethnicity, race, height and weight. BMI will be calculated from height and weight and recorded with 1 decimal point.

4.4 Medical/Surgical History

Medical/surgical history will include all relevant diseases and operations within 2 months prior to screening as judged by the Investigator.

4.5 Prior and Concomitant Medications

Medications are classified as prior if the stop date was before or on the day of the first dose administration (pre-dose) and as concomitant if ongoing on the day of the first dose administration, stopped after the first dose administration or started after the first dose administration.

Any use of concomitant medication from screening until the end-of-study visit will be documented appropriately. Relevant information (i.e., name of medication, dose, unit, frequency, dose form, route, start and stop dates, reason for use) will be recorded.

4.6 Safety Variables

4.6.1 Adverse Events

An AE is defined as any untoward medical occurrence in a subject administered a medicinal product and which does not necessarily have a causal relationship with this treatment. An AE can therefore

Statistical Analysis Plan

CX842A2106

Version 1.0 final, 2023 Jan 16

be any unfavourable and unintended sign (including an abnormal laboratory finding), symptom, or disease temporally associated with the use of a medicinal product, whether or not considered related to the medicinal product.

Definitions for the different types of AE including the definition for Serious Adverse Events (SAEs), Adverse Reaction (AR), Serious Adverse Reaction (SAR) and Serious Unexpected Adverse Reaction (SUAR) are given in section 11.4 of the CSP.

The following variables will be collected for each AE and SAE:

- Start date and time
- · Stop date and time
- Whether the AE is serious
- Intensity (Mild, Moderate, Severe)
- Causality (Probable, Possible, Unlikely
- Assessment of outcome (Recovered/resolved, Recovering, resolving, Recovered/resolved with sequelae, Not recovered/not resolved, Fatal, Unknown)
- Action taken with study treatment (Dose decreased, Dose not changed, Dose reduced, Drug interrupted, Drug withdrawn, Not applicable, Unknown)

An AE is considered causally related to the use of the IMP when the causality assessment is probable or possible.

AEs will be followed up until resolution or end-of-study visit, whichever comes first.

4.6.2 Laboratory Evaluations

Blood and urine samples for the assessment of safety and eligibility will be collected as shown in Table 3. Safety laboratory values will be specified and documented as Normal, Abnormal NCS, or Abnormal CS. Abnormal post-dose findings assessed by the Investigator as CS will be reported as AEs.

Table 3. Safety Laboratory Parameters

Category	Parameter			
Clinical chemistry	Alanine aminotransferase (ALT)			
	Albumin			
	Alkaline phosphatase (ALP)			
	Aspartate aminotransferase (AST)			
	Bilirubin (total and conjugated)			
	Calcium			
	Creatinine			
	Glucose			
	Phosphate			
	Potassium			
	Sodium			
	Urea			
Hematology	Erythrocyte count			
	Leukocyte count with differential count			
Statistical Analysis Plan				
CX842A2106				
Version 1.0 final, 2023 Jan 16				

14(24)

Category	Parameter				
	Hematocrit (B-EVF)				
	Hemoglobin (Hb)				
	Mean corpuscular volume (MCV)				
	Mean corpuscular hemoglobin (MCH)				
	Platelet count				
Coagulation	Activated Partial Thromboplastin Time (APTT)				
	Prothrombin Complex International Normalized Ratio (PK[INR])				
Urinalysis (dip stick)	Erythrocytes				
	Glucose				
	Ketones				
	Leukocytes				
	Nitrite				
	рН				
	Protein				
	Specific gravity				
	Urobilinogen				
Confirmation of menopause (at screening, postmenopausal females only)	Follicle stimulating hormone (FSH)				
Pregnancy test (female subjects of childbearing potential only)	Urine pregnancy test.				

4.6.3 Physical Examination

A complete physical examination will include assessments of the head, eyes, ears, nose, throat, skin, thyroid, neurological, lungs, cardiovascular, abdomen (liver and spleen), lymph nodes and extremities.

Any abnormalities will be specified and documented as CS or NCS. Abnormal post-dose findings assessed by the Investigator as clinically significant will be reported as AEs.

4.6.4 Vital Signs

Vital signs will include systolic and diastolic blood pressure, pulse rate and body temperature. Any vital signs outside of normal ranges will be specified and documented as CS or NCS. Abnormal post-dose findings assessed by the Investigator as CS will be reported as AEs.

4.6.5 ECGs

A 12-lead ECG will be recorded at admission (day -1), after 4 hours (with a time window of 30 min) on Day 1 and at discharge from the study i.e., 72 hours after dosing (which is on day 4 of the study). The ECG measurements must occur after the PK and safety blood samples have been collected.

The following variables will be recorded:

Statistical Analysis Plan

CX842A2106

Version 1.0 final, 2023 Jan 16

- Resting Heart Rate
- PQ/RR
- QRS
- QT
- QTcF

Any post-dose abnormalities will be specified and documented as CS or not NCS. Abnormal post-dose findings assessed by the Investigator as CS will be reported as AEs.

4.7 Pharmacokinetic Assessments

Blood sampling time points for PK analyses and their allowed sampling time windows are detailed in section 8.1, 11.1 and 11.3.1 of the CSP. The actual blood sampling time points will be recorded in the CRFs

Plasma samples for determination of plasma concentrations and PK characterization of linaprazan glurate and linaprazan will be analyzed

The PK

parameters to be determined are listed and defined below. For further details regarding the calculation of these parameters, see section 5.6.

PK parameters:

The following PK parameters will be obtained or calculated from the plasma concentration-time data of linaprazan glurate and linaprazan, after dosing with Treatment A (Reference formulation, fasting condition), B (Test formulation, fasting condition) and C (Test formulation, fed condition) if sufficient data is available:

- AUCinf (the area under the concentration-time curve from time zero extrapolated to infinity)
- AUClast (area under the concentration-time curve from time zero to time of last measurable observed concentration)
- Cmax (maximum observed concentration)
- \bullet T_{lag} (Delay between the time of dosing and the time of appearance of plasma concentration), if applicable
- T_{max} (time to maximum observed concentration)
- λ_z (elimination rate constant)
- T_{1/2} (terminal half-life)
- CL/F (apparent total clearance)
- V/F (apparent volume of distribution)

Additional PK parameters may be determined if deemed appropriate.

How the PK parameters are determined are further described in section 5.6

Statistical Analysis Plan

CX842A2106

Version 1.0 final, 2023 Jan 16

5. Analysis Methods

All statistical analyses will be performed using SAS® (Version 9.4 or higher, SAS Institute Inc., Cary, NC, USA).

All PK analyses will be performed on individual plasma concentration-time data by non-compartmental analysis (NCA) using the software Phoenix WinNonlin® 8.3 or higher (Certara Inc, Princeton NJ, United States). An interim evaluation of PK and safety data will be performed when all subjects finalized sampling after their first dose.

All final statistical and PK analyses will be performed after this SAP is finalized and approved, the Clean File Report including decisions on analysis sets has been signed, and the database has been locked.

5.1 Analysis Sets

5.1.1 Full Analysis Set (FAS)

The full analysis set (FAS) will consist of all subjects who have been randomized and received at least 1 dose of IMP and who provided at least 1 post-baseline assessment of data.

The FAS will also be used for all safety analyses.

5.1.2 PK Analysis Set (PKAS)

The PK analysis set (PKAS) will consist of all subjects who received at least 1 dose of linaprazan glurate and provided an evaluable plasma concentration profile, and who have no AEs or protocol deviations judged to affect the PK analysis. Individual PK values may be excluded from the analysis as specified in section 5.6. Relative bioavailability will be estimated for individuals who have provided at least two PK profiles for the comparison of interest (A and B) or (B and C).

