5.6 Pharmacokinetic Analyses

The PK analysis will be performed based on the PK analysis set and Exploratory PK analysis set. All PK analyses will be performed according to the actual treatment and dose received. Actual sampling time points relative to dosing will be used in the calculations. Pre-dose concentration values will be excluded from the NCA and set to 0.

Statistical Analysis Plan

CX842A2106

Version 1.0 final, 2023 Jan 16

The parameters to be determined in the study are presented in section 4.7. Parameters directly derived from the plasma concentration – time plot are not further described (i.e. C_{max} , t_{max}), but all other calculations to be performed are described in detail below. Missing sample around the anticipated tmax may be flagged as "not accepted" upon decision by the pharmacokineticist.

For subjects with insufficient PK data available leading to an extrapolated AUC (%Extrap AUC) exceeding 20%, the parameters depending on λ_7 (AUC_{inf}, $t_{1/2}$, CL/F, and V/F) will not be reported.

Estimation of the terminal elimination rate constant (λ_z)

The terminal elimination rate constant (λ_z) is calculated by log-linear regression of the terminal portion of the plasma concentration time profile. At least three observations will be used to estimate λ_z and the data points used in each estimation are indicated in the individual PK profiles. Data points for calculation of $t_{1/2}$ via λ_z are selected based on visual inspection of log-concentration-time plots of individual profiles and adjusted if needed. Any exclusion of data points in the terminal phase for this estimation should be clearly justified in the PK analysis log.

The adjusted R^2 should be considered in the selection of samples for calculation of λ_z and preferably exceed a value of 0.8. If λ_z cannot be reliably estimated, resulting in a low value of R^2 , it will be flagged as "not accepted" and the associated parameters (AUC_{inf}, $t_{1/2}$, CL/F, and V/F) may be reported as "not determined".

Use of λ_z values obtained from data spanning less than three half-lives is permissible on the judgement of the pharmacokineticist provided that the resulting extrapolated area is not more than 20% of the total AUC determined. The % of extrapolated AUC will be presented for all subjects.

Area under the plasma concentration-time curves (AUCs)

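### As written, SAP 5.1.2 removes a whole subject from the PK analysis set for a PK-affecting event in one period, which conflicts with the SAP's own per-comparison rule

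*SAP*

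**What the plan says.** SAP 5.1.2 builds the PKAS from subjects with at least one dose and an evaluable profile, "who have no AEs or protocol deviations judged to affect the PK analysis". It then adds: "Individual PK values may be excluded from the analysis as specified in section 5.6". It ends with a rule for each comparison: "Relative bioavailability will be estimated for individuals who have provided at least two PK profiles for the comparison of interest", naming A with B, or B with C.

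SAP 4.2 classifies the subject but excludes data: "If a subject is classified with a major protocol deviation, it will lead to exclusion of data from the PK analysis set". One of its listed major deviations belongs to a single dose and a single profile: "Vomiting or diarrhoea within 6 hours after dosing which could render the plasma concentration-time profile unreliable".

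SAP 5.3.1 states that the statistical analysis uses all the data available. SAP 5.6.1 runs the primary fixed-effects model on the PKAS and restricts it to subjects who completed the study. The supplementary random-effects model has no such restriction.

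**The concern.** In a three-period crossover, a PK-affecting event usually spoils one profile. Under the membership sentence in 5.1.2, a subject who vomits after fed Treatment C but has sound A and B profiles is outside the PKAS and adds nothing to the formulation comparison B/A. Under the last sentence of the same section, that subject qualifies for B/A. Two statisticians could build different primary datasets from the same data, both following the SAP.

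Precision is at stake, and so is the clarity of the population for each comparison. Under the literal reading, B/A is restricted according to what happened under C, a treatment that is not part of it. The trial is open-label, there is an interim look at PK data after the first dose, and the analysis sets are decided in the Clean File Report (SAP 3.3 and section 5). The unit of exclusion should therefore be fixed in advance.

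**Working it through.** **The plan's own figures.** SAP 3.4.1 gives 84 screened, about 37% screening failure, 54 randomized and at least 42 evaluable. 84 × (1 − 0.37) = 52.9 and 54 / 0.63 = 85.7, which agree with 54 and 84 at the stated precision. Going from 54 to 42 allows a loss of 12/54 = 22.2%. The SAP gives no within-subject CV and no rate of PK-affecting events, so both are assumptions below.

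**Is there a by-period route?** 5.1.2 lets individual values be excluded only as 5.6 specifies. Section 5.6 deals with pre-dose values, missing samples around tmax, and parameters that depend on λz (poor fit, or more than 20% of AUC extrapolated). It has no provision for AEs or protocol deviations.

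**What is recoverable for one affected period under the two-profile rule**

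| Event only under | Profiles left | Direct pair left |
|---|---|---|
| A | B, C | C/B |
| B | A, C | none |
| C | A, B | B/A |

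**Expected subjects per comparison.** Assume the same rate p in every period, independent events and no other losses. Whole-subject exclusion leaves 54(1 − p)³. Dropping only the affected profile leaves 54(1 − p)² direct pairs per comparison. The last two columns are binomial probabilities of at least 42.

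| p | Whole subject | Affected profile only | Difference | P(≥42), whole subject | P(≥42), profile only |
|---|---|---|---|---|---|
| 2% | 50.8 | 51.9 | 1.0 | 1.000 | 1.000 |
| 5% | 46.3 | 48.7 | 2.4 | 0.963 | 0.998 |
| 8% | 42.0 | 45.7 | 3.7 | 0.583 | 0.938 |
| 10% | 39.4 | 43.7 | 4.4 | 0.261 | 0.786 |

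**Variance in the SAP's fixed-effects model.** The design has subject, period and treatment effects, with 54 subjects balanced over six sequences. Variances are multiples of the within-subject variance; with no loss, each contrast has 2/54 = 0.0370. Suppose 6 subjects have one affected period each. Whole-subject exclusion gives 2/48 = 0.0417 for both contrasts. Dropping only the affected profile gives:

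| Affected treatment | B − A | C − B |
|---|---|---|
| A | 0.0405 | 0.0370 |
| B | 0.0405 | 0.0405 |
| C | 0.0370 | 0.0405 |
| spread evenly | 0.0393 | 0.0393 |

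Where the direct pair survives, the CI half-width on the log scale under whole-subject exclusion is √(0.0417/0.0370) = 1.06 times as wide. Where it does not, the ratio is √(0.0417/0.0405) = 1.01. With 12 affected subjects spread evenly, the variances are 0.0476 and 0.0418, about 14% more under whole-subject exclusion.

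**On the ratio scale.** The 90% limits are the GMR divided and multiplied by exp(t × s√(2/n)), where t is the 95th percentile on 2n − 4 df and s = √ln(1 + CV²). Going from n = 54 to n = 48 moves the multiplier from 1.065 to 1.069 at CV 20%, from 1.098 to 1.105 at 30%, and from 1.163 to 1.174 at 50%.

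**The case against.** The best defence is that whole-subject exclusion is not the settled rule. Section 5.1.2 asks for one evaluable profile and then qualifies subjects by comparison. Section 4.2 excludes data, not the subject, and describes vomiting or diarrhoea as making a profile unreliable. Section 5.3.1 uses all available data. Exclusion is also a judgement, decided and justified at the clean file meeting before database lock, and nothing obliges that meeting to discard sound periods. This stands as a reason not to claim that the plan certainly drops such subjects. It does not remove the problem: none of these sentences overrides the membership criterion, and a subject outside the PKAS has no profiles in the primary model.

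Some listed deviations, such as significant non-compliance or a prohibited medication, can span periods, and removing the whole subject may then be right. That also stands, and the fix allows for it.

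The cost is modest at low rates, the plan already allows for losing 12 of 54 subjects, and SAP 3.5 permits additional subjects after withdrawals. This stands too, and it limits the severity.

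A reader might go further and infer that sound profiles are lost to both primary comparisons, or that B/A will be biased by meal reactions. The document supports neither. At most one direct pair per affected subject is recoverable, and the other contrast changes only slightly. The SAP gives no rate of events under C and nothing that links a reaction to C with a subject's B/A ratio.

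**Conclusion.** The point holds as a contradiction about the unit of exclusion, in which the literal reading of 5.1.2 is the worse option. It is worth correcting before database lock but does not threaten the trial at low event rates. The avoidable loss is about 1 subject per comparison at 2% per period, 2.4 at 5% and 4.4 at 10%. The target of 42 comes into doubt under whole-subject exclusion only near 8–10%. These figures rest on assumed rates that are equal and independent across periods, with no other dropout. With 6 of 54 subjects affected, whole-subject exclusion gives the larger variance for both contrasts whichever treatment is affected, though by little where the direct pair is gone anyway.

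The completers-only restriction in 5.6.1 belongs to the same contradiction. A subject with sound A and B profiles who leaves before C qualifies under 5.1.2 but not under 5.6.1. A subject who attends all three periods with one spoiled profile may or may not count as a completer.

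The definition of the exploratory PK analysis set is not visible in the text available, so nothing is concluded from it. The primary comparisons use the PKAS.

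**What to change.** - **5.1.2 and 4.2:** state that an AE or major deviation judged to affect PK excludes only the profile of the affected period. Exclude the whole subject only when the deviation affects all periods, for example sustained non-compliance.
- **5.6.1:** reconcile the completers-only restriction with the two-profile rule, so that subjects with evaluable A and B profiles, or B and C profiles, enter the primary model for that comparison.

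The cost is SAP wording only. The specified model can be fitted with unequal numbers of profiles per subject. The small downside is that the number of subjects may differ between B/A and C/B, so each table should show its own n.
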